### **3.3 Duration of Study Participation**

The study duration per subject will be approximately 20 minutes including the time to prepare Lumason™ contrast agent, perform the pre-contrast imaging, and perform the CEUS, as well as the 60 minute monitoring period after the first and second injection of Lumason™.

CEUS will be performed at the time HII is first suspected or diagnosed. A second CEUS may be performed at short-term follow-up (approximately within 1-2 weeks from the first scan) for a total of two CEUS exams of 1 hour and 20-minute duration each.

Study participation will be complete when the 60 minute monitoring period of the last CEUS to be performed (after the first CEUS in patients who undergo one exam, or after the second CEUS is complete in patients who undergo two exams).

### **3.4 Total Number of Study Sites/Total Number of Subjects Projected**

The study will be conducted at one site, The Children's Hospital of Philadelphia. It is expected 200 subjects will be enrolled to produce 100 evaluable subjects.

### **3.5 Study Population**

#### **3.5.1 Inclusion Criteria**

1. Males and females aged 1.5 years or younger with open fontanelles and known or suspected hypoxic ischemic injury
2. Post menstrual age of 34 weeks or older
3. Patient in the CHOP NICU or PICU
4. Parental permission

## **4 STUDY PROCEDURES**

### **4.1 Screening**

- Identify patients with suspected or diagnosed hypoxic ischemic injury
- Review of medical records (for inclusion and exclusion criteria)
- Discussion of the case with neonatologists and study team to determine eligibility
- If subject is considered eligible, written consent can be obtained at this stage by PI, co-investigator, or neonatologist co-investigator
- Coordinate cranial ultrasound schedule

### **4.2 Study Treatment Phase**

Subjects enrolled to this clinical trial are anticipated to receive the study drug and have CEUS imaging conducted in the ICU setting. In this case, the study drug and US imaging unit will be brought to the ICU for study drug administration and imaging. Any clinically indicated non-contrast cranial ultrasounds be performed prior to contrast-enhanced cranial ultrasound so as not to delay clinical care.

#### Pre-injection documentation

Prior to injection, Vital signs and baseline assessment will be recorded and documented from the medical record and clinically in-place monitoring. Baseline assessment will consist on neurological status as described in the clinical evaluations recorded in the medical chart prior to intervention.

#### Pre-injection evaluation

The exam will include a pre-contrast injection evaluation with FDA-approved technologies (e.g. gray-scale ultrasound, Doppler ultrasound, microvascular imaging) to assess anatomical structures and guide contrast evaluation. This will last approximately 5 minutes.

#### CEUS scan

CEUS duration is of approximately 15 minutes.

CEUS will be performed at the time HII is first suspected or diagnosed. A second CEUS may be performed at short-term follow-up (approximately within 1-2 weeks from the first scan) for a total of two CEUS exams of 1 hour and 20-minute duration each.

Study participation will be complete when the 60-minute monitoring period of the last CEUS to be performed (after the first CEUS in patients who undergo one exam, or after the second CEUS is complete in patients who undergo two exams).

For those neonates/infants not undergoing hypothermia therapy, the first CEUS scan will be performed at the time HII is first suspected or diagnosed and the second CEUS scan will be performed within 24 hours of clinically indicated MRI. It is part of standard of care to obtain a clinically indicated MRI as follow-up of diagnosed or suspected hypoxic ischemic injury.

#### 60-minute monitoring period

The study team, who are composed of personnel trained in recognizing signs of infusion reaction, will conduct the 60 minute monitoring period and record any untoward reaction that may be related to the infusion of the contrast drug. The 60 minute monitoring post-CEUS will be conducted by study team members.

Vital signs will be recorded and documented from the medical record and clinically in-place monitoring at 1) 30 minutes post-scanning, and 2) 60 minutes post-scanning. During monitoring, subjects will be assessed for rash, allergic reactions, anaphylaxis, and abrupt deviations from the subject's baseline hemodynamic parameters trend not related to medical intervention.

### Adverse event assessment and documentation

Adverse events will be recorded at 1) 60 minutes post-scanning when the monitoring period is completed, and 2) through 48 hours post-scanning, with documentation at 48 hours post-scanning if no adverse event presents until this point. During the 48-hour AE assessment period, the following AEs of special interest will also be assessed:

- a. worsening cardiopulmonary status,
- b. worsening pulmonary hypertension, which may be suggested by new requirement of nitric oxide use, elevated pulmonary artery pressures on echocardiography, or differential limb pulse oximetry measurements,
- c. worsening neurological status, and
- d. serious gastrointestinal complications

#### **4.2.1 CEUS #1**

- Obtain consent prior to scheduled CEUS exam (if not previously obtained by, PI, co-investigator, or neonatologist co-investigator)
- Record vital signs and baseline assessment prior to injection of contrast
- Perform pre-contrast injection evaluation.
- CEUS scan performed at the time HII is first suspected or diagnosed
- Monitor subject for 60 minutes following the CEUS scan for documentation and treatment of potential adverse events
- Documentation of any adverse events through 48 hours post-scanning

#### **4.2.2 CEUS #2**

A second CEUS may be performed at short-term follow-up (approximately within 1-2 weeks from the first scan) for a total of two CEUS exams of 1 hour and 20-minute duration each.

- Record vital signs and baseline assessment prior to injection of contrast
- Perform pre-contrast injection evaluation.
- CEUS scan performed on the same day of MRI exam
- Monitor patient for 60 minutes following the scan for documentation and treatment of potential adverse events

Documentation of any adverse events through 48 hours post-scanning

Study participation will be complete when the 60-minute monitoring period of the last CEUS to be performed (after the first CEUS in patients who undergo one exam, or after the second CEUS is complete in patients who undergo two exams).

The study team will not use sedation or general anesthesia to conduct the research CEUS scans. The lowest mechanical index (MI) possible will be implemented in both CEUS, with a maximum MI value <0.2.

The results of the CEUS imaging will be collected for research purposes only. The results of the CEUS will not be used to direct clinical care decisions, without

confirmation of diagnosis by another medically established diagnostic product or procedure

#### **4.3 Concomitant Medication**

No concomitant medications will be recorded, with the exception of rescue medications, as noted below.

#### **4.4 Rescue Medication Administration**

All the rapid response equipment and resuscitation staff are readily available 24/7 in the intensive care unit setting at Children's Hospital of Philadelphia. In the rare event that a significant allergic reaction occurs, or anaphylaxis results following injection of Lumason™, standard clinical medication to treat the subject will be administered. For presumed allergic reactions, medications may include intravenous diphenhydramine and bolus corticosteroids (prednisolone), based on clinical care. For anaphylaxis, medications may include epinephrine as well as fluid and oxygen administration for emergency treatment, based on clinical care decision making and on the severity of symptoms. Any severe allergic or anaphylactic reaction will be reported to both the IRB and the FDA.

#### **4.5 Subject Completion/Withdrawal**

Subjects' families may withdraw their child from the study at any time without prejudice to their child's care. A study investigator may withdraw a subject to protect the subject for reasons of safety or for administrative reasons. It will be documented whether or not each subject completes the clinical study. If the Investigator becomes aware of any serious, related adverse events after the subject completes or withdraws from the study, the adverse events will be recorded and reported.

##### **4.5.1 Early Termination Study Visit**

A subject may be withdrawn by a parent prior to or during a CEUS scan, provided the 60 minute monitoring is completed after injection of the investigational drug. The CEUS examination will be terminated if there is a deterioration in the subject's clinical status during imaging.

##### **4.5.2 Review of medical records from EPIC and/or other sources**

- Date of birth
- Weight
- Clinical diagnosis
- Treatment history (medications, chemotherapy, antibiotics, steroids)
- Surgical history
- Pathology report

#### **4.5.3 Review of diagnostic images from the PACS (iSite Radiology or iSite Enterprise)**

- Review of cranial ultrasound and CEUS images (iSite)
- Review of available MRI images

### **5 STUDY EVALUATIONS AND MEASUREMENTS**

The results of the pre-contrast injection and CEUS imaging will be collected for research purposes only. The results of the CEUS will not be used to direct clinical care decisions, without confirmation of diagnosis by another medically established diagnostic product or procedure.

#### Qualitative analysis

Visual rating by 2 teams consisting of primary investigator and second radiologist (co-investigator). Each scan will be rated for diagnostic quality and qualitative rating of cranial perfusion. The visual rating scale used will be: 0 (absent flow), 1 (decreased flow), 2 (normal flow), 3 (increased flow).

#### Quantitative analysis

Qontrast (Bracco Diag Inc., 510K regulatory status granted in 2004) contrast quantification software or similar software will be used to analyze the obtained CEUS scans. For each scan, wash-in and wash-out curves will be generated to quantify the rate of wash-in, time to peak intensity, peak intensity, and area under the curve.

The CEUS scans will be interpreted by the sponsor-investigator, and a second interpretation by a “second reader” in Radiology, who is part of a group of radiologists with sufficient training and expertise to read CEUS scans.

#### Monitoring After Investigational Drug Administration:

The monitoring post-administration will encompass 60 minutes, during which time the subject will be observed for the occurrence of infusion reactions. Any concern by the investigative team or attending staff for severe allergic reaction or anaphylaxis will be managed as all similar reactions are managed as part of clinical care, with close observation and treatment as clinically indicated, which may include diphenhydramine, corticosteroids, fluids, oxygen and epinephrine. Post-infusion reactions will be recorded and reported following established IRB and FDA reporting guidelines.

### **6 STATISTICAL CONSIDERATIONS**

Up to 100 evaluable patients should be adequate for assessment of clinical feasibility and optimization of protocol. Qualitative analysis will be used as detailed above. Quantitative analysis will be performed by drawing a region of interest in brain segments and compared to control subjects (those with suspected or at risk of HII but turns out to be normal on imaging and clinical evaluation) using non-parametric Wilcoxon testing.

The study will optimize current techniques in the application of contrast ultrasound. For instance in brain imaging, the optimal plane in which to obtain the contrast perfusion kinetics curve is suggested but not established. The region of interest placement for perfusion kinetics quantification is also suggested by few publications, but not established as the standard practice. All this is part of the optimization process that is pivotal to improving the current contrast ultrasound techniques.

Specific analysis plan consists of both qualitative and quantitative assessment in which description of focal perfusion deficit or lesion, for instance, is reported in correlation with clinical information. Perfusion abnormalities will be qualitatively evaluated (absent – 0, mild hypoperfusion – 1, normal – 2, hyperperfusion – 3) and quantitatively (region of interest placed on brain regions for acquisition of wash-in curves using QLab or Qontrast or other similar software). These abnormalities will be correlated to MRI findings as gold standard, non-contrast ultrasound, and clinical information (neurologic exam, hemodynamics, behavioral outcomes) between serial exams. For extremely injured brain cases, nuclear scan (for diagnosis of brain death) instead of MRI may be performed as part of gold standard

The sample size will be based on the available cases, and based on the current number of patients presenting to Children's Hospital of Philadelphia neonatal or pediatric intensive care unit with clinical suspicion for hypoxic ischemic injury. It is estimated that the study will achieve a sample size of up to 50 neonates and infants per year for up to two years.

Baseline and demographic characteristics will be summarized using descriptive measures. Statistical analysis will consist of comparing diagnostic tests, in this case conventional grayscale ultrasound and contrast ultrasound, on each patient using the McNemar's test. Differences between perfusion before and after resuscitation (in the setting of hypoxic ischemic injury) will be evaluated with the Wilcoxon signal rank test for related samples.

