### **6.2 Secondary Endpoints**

Quantitative analysis of perfusion abnormalities in correlation with clinical MRI results. This will be achieved by quantitative analysis, identifying regions of interest and generating time intensity curves.

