## **6.4 Sample Size and Power**

Power analyses indicate that the study is sufficiently powered to detect group perfusion differences. For example, given a basal ganglia PE mean value in the control group of 1.37 (SD = 0.23) and in the patient group of 0.96 (0.09), with an alpha p = 0.05, power to detect group differences with a sample of 25 per group approaches 1.00. As another example, given a peak cortical perfusion mean value in the control group of 2.46 (SD = 1.96) and in the patient group of 0.69 (0.20), with an alpha p = 0.05, power to detect group differences with a sample of 50 per group approaches 0.84.

Given a sample of about 100 imaged patients, pilot data suggest that approximately one-half will show abnormal perfusion, thus providing a final sample of approximately 50 patients with abnormal perfusion and 50 patients with normal perfusion. The above sample sizes were used to compute the power to detect group differences in the ratio of basal ganglia to cortex perfusion, using means and standard deviations obtained from the pilot sample (see Preliminary Data).

Power analyses indicate that the study is sufficiently powered to detect group perfusion differences. For example, given a basal ganglia PE mean value in the control group of 1.37 (SD = 0.23) and in the patient group of 0.96 (0.09), with an alpha p = 0.05, power to detect group differences with a sample of 50 per group approaches 1.00. As another example, given a peak cortical perfusion mean value in the control group of 2.46 (SD = 1.96) and in the patient group of 0.69 (0.20), with an alpha p = 0.05, power to detect group differences with a sample of 50 per group approaches 0.85.

An interim statistical analysis may be considered to review image quality and comparisons between the results of each subject's CEUS scans and available clinical US exams, to better inform the number of subjects required for statistical significance.

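### The quantitative patient-control comparison spans four curve parameters and more than one brain region, with no deciding contrast, no multiplicity rule and no exploratory label, while Section 6.4 claims adequate power

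*Combined protocol and SAP*

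**What the plan says.** The quantitative analysis is the secondary endpoint. Section 6.2 describes it as: "This will be achieved by quantitative analysis, identifying regions of interest and generating time intensity curves". The pieces that define it are spread over three places.

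- **Parameters.** Section 5, Quantitative analysis: the software's curves from every examination are used to "quantify the rate of wash-in, time to peak intensity, peak intensity, and area under the curve". That is four parameters per curve.
- **Regions and test.** Section 6: "Quantitative analysis will be performed by drawing a region of interest in brain segments and compared to control subjects", where controls are infants with suspected HII, or at risk of it, who prove normal on imaging and clinical evaluation. The comparison is made "using non-parametric Wilcoxon testing". The segments are plural and are neither counted nor listed.
- **Contrasts and alpha.** Section 6.4 gives two worked examples, basal ganglia PE and peak cortical perfusion, each at alpha 0.05. It also says the sample sizes were used to compute "power to detect group differences in the ratio of basal ganglia to cortex perfusion, using means and standard deviations obtained from the pilot sample". It opens with: "Power analyses indicate that the study is sufficiently powered to detect group perfusion differences", and repeats that sentence later.

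Section 2.1 adds a further candidate: the primary objective is a gray versus white matter perfusion ratio. The primary endpoint in Section 6.1, however, is the qualitative reading against MRI.

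**The concern.** The plan leaves open which of several quantitative comparisons would show that perfusion differs between injured and normal infants. A reader who follows it can test four parameters in two or more regions, plus a ratio, and report whichever falls below 0.05. Nothing in the text rules that out, and the power statement in Section 6.4 invites a confirmatory reading of the result. What is at stake is the credibility of a reported group difference in CEUS perfusion. With several unranked tests, one nominally significant result is weaker evidence than its p-value suggests.

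This is separate from the open choice of imaging plane and region placement that Section 6 calls optimization. Fixing both in advance would still leave several parameters in several regions.

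**Working it through.** **Inputs from the documents**

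- Four curve parameters (Section 5).
- At least two regions, basal ganglia and cortex (Section 6.4); Section 6 gives no count.
- Alpha 0.05, stated only in the power examples, with no sidedness (Section 6.4).
- About 50 infants per group (Section 6.4).
- Control versus patient values (Section 6.4): basal ganglia PE 1.37 (SD 0.23) vs 0.96 (0.09); peak cortical perfusion 2.46 (SD 1.96) vs 0.69 (0.20).

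**Assumptions, not in the documents**

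- Every test is two-sided at 0.05.
- All null hypotheses are true.
- The tests share a common correlation ρ.
- Any positive result is read as a group difference.

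**Step 1. The plan's own power figures.** Power = Φ(difference / SE − 1.96), with SE = √(SD₁²/n + SD₂²/n).

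- Basal ganglia, 25 per group: SE = √(0.23²/25 + 0.09²/25) = 0.0494; 0.41/0.0494 = 8.30; power 1.00. This reproduces "with an alpha p = 0.05, power to detect group differences with a sample of 25 per group approaches 1.00".
- Cortex, 50 per group: SE = √(1.96²/50 + 0.20²/50) = 0.279; 1.77/0.279 = 6.35; power 1.00. Section 6.4 states 0.84 and later 0.85 from the same inputs. Neither reproduces. Even with SD 1.96 in both groups the result is 0.995.

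The false-positive calculation below does not use these power figures. The cost of the fix does.

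**Step 2. Chance of at least one false positive among k tests.** For independent tests it is 1 − 0.95^k:

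- k = 2: 1 − 0.9025 = 0.0975
- k = 4: 1 − 0.8145 = 0.1855
- k = 8: 1 − 0.6634 = 0.3366

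For correlation ρ it is 1 − ∫ [Φ((1.96 − √ρ g)/√(1−ρ)) − Φ((−1.96 − √ρ g)/√(1−ρ))]^k φ(g) dg.

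| Tests | ρ = 0 | ρ = 0.5 | ρ = 0.8 | ρ = 0.9 |
|---|---|---|---|---|
| 2 (the two Section 6.4 examples) | 9.8% | 9.1% | 7.8% | 7.0% |
| 4 (four parameters, one region) | 18.6% | 15.6% | 11.4% | 9.4% |
| 8 (four parameters, two regions) | 33.7% | 25.0% | 15.7% | 11.9% |

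Simulated rank-sum tests at 50 per group with ρ = 0.5 gave 15.8% for four tests and 25.6% for eight, in line with the table.

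**Step 3. Power under a strict adjustment.** Take 0.05/12, harsher than the eight-test family needs. With the Section 6.4 means and SDs and normal data, simulated rank-sum power at 50 per group is 1.00 for basal ganglia PE and about 0.996 for cortex.

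If the stated cortical power were right instead, the same adjustment would be expensive. The two-sided critical value at 0.05/12 is 2.865. From 0.84, Φ(0.994 + 1.960 − 2.865) = Φ(0.089) = 0.54. From 0.85, Φ(1.036 + 1.960 − 2.865) = Φ(0.131) = 0.55.

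**The case against.** The strongest reply is that this is a secondary endpoint in a study whose sample Section 6 justifies by feasibility and optimization. The primary endpoint is qualitative, and CEUS results may not direct care without confirmation by another established method. Formal error control over secondary measures in such a study is not obligatory, and the documents never claim a 5% familywise rate. That stands, and it limits the weight of the point. It does not remove it: the only power calculation in the protocol is for these quantitative group differences, and Section 6.4 twice calls the study sufficiently powered for them. If the tests are exploratory, the plan should say so.

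Three stronger readings are tempting and are not supported.

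- **A reader might infer a definite false-positive rate of 16-25%.** That needs four to eight tests and a correlation of 0.5. The documents give neither.
- **A reader might infer that every parameter is tested in every region at 0.05.** Section 5 says what the software will quantify, not what will be tested. The Wilcoxon sentence in Section 6 sets no alpha; 0.05 appears only in the power examples. A family of twelve would also need a ratio for every parameter, which no section proposes.
- **A reader might use the Figure 2 table as proof that parameters point in opposite directions.** In table order, wash-in slope is 10.59 then 1.3, and area under the curve 1125.76 then 1230.23. The caption, however, says 2B has both quicker wash-in and higher area under the curve than 2A. Table and caption conflict, and these are single readings, not group data. No weight is put on them here.

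**Conclusion.** The concern holds as a gap in the secondary analysis. The plan has several candidate quantitative contrasts, none designated as deciding, with no multiplicity rule and no exploratory label, alongside a claim of adequate power. Under the stated assumptions the false-positive chance is about 7-10% for the two Section 6.4 examples and about 9-34% for four to eight tests over correlations from 0.9 to 0. Every scenario in the table exceeds 5%, but the exact figure cannot be taken from the documents. This is not a failed primary test, and it does not show that the planned comparison would give a wrong answer.

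**What to change.** In Sections 6.2 and 6.3, name one curve parameter and one region or ratio as the deciding contrast, patients versus controls, Wilcoxon at two-sided 0.05. One candidate is peak enhancement (the apparent meaning of PE, which the abbreviation list does not define) as the basal ganglia to cortex ratio that Section 6.4 cites for sizing. That choice must first be reconciled with the gray/white matter ratio in Section 2.1. Section 6.4 gives no mean or SD for the basal ganglia to cortex ratio, so these should be added.

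For the remaining parameter-by-region comparisons, either list them and apply Holm's procedure, or label them exploratory and report estimates with confidence intervals and no significance claim. If one overall 5% level is wanted, run the Holm step only after the deciding contrast is significant. In Section 6.4, limit the power claim to the named contrast, and separately correct the cortical power figure.

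The cost is a few sentences, with no added infants, scans or readers. Nominal p-values below 0.05 on other parameters could no longer be claimed as significant on their own. The deciding contrast keeps the full 0.05. For the others, the Section 6.4 means and SDs leave power of about 0.995 or more at 50 per group even at 0.05/12. This assumes normal data, a rough fit for cortex: mean 2.46 with SD 1.96 puts about 10% of control values below zero.

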## Protocol Synopsis

Study Title	Improved Diagnosis and Prognostication of Hypoxic Ischemic Injury in Neonates and Infants Using Contrast-Enhanced Ultrasound
Funder	Children's Hospital of Philadelphia
Clinical Phase	Phase II
Study Rationale	
Neonates presenting with neurologic symptoms require rapid, non-invasive imaging with high spatial resolution and tissue contrast. Magnetic resonance imaging (MRI) is currently the most sensitive and specific neuroimaging modality for evaluation of neonatal neurological diseases. This modality does come with several challenges in the neonatal population, namely the need to transport a possibly critically sick neonate to the MRI suite and the necessity of the neonate to remain still for a significant length of time, occasionally requiring sedation. Cranial ultrasound has provided neuroradiologists and clinicians with an invaluable neuroimaging modality that allows a rapid, bedside point of care evaluation without ionizing radiation. The major drawback of cranial ultrasound is its lower sensitivity and specificity for subtle/early lesions. Contrast enhanced ultrasound (CEUS) has the potential to improve sensitivity and specificity for a variety of neonatal neurological diseases and expand the indications for cranial ultrasound.
 
There is no current diagnostic tool with high soft tissue contrast that can assess brain perfusion of neonates and infants at the bedside. Critically ill neonates cannot be transported easily down to the magnetic resonance suite, and even when transported, ultrafast sequences are performed (which lack perfusion imaging) due to their clinical condition. In the case of neonatal hypoxic ischemic injury, our preliminary evidence has shown that contrast-enhanced ultrasound (CEUS) of the brain delineates areas of injury, as the perfusion to the injured regions of the brain become altered. Extensive literature exists in regard to the value of perfusion imaging in brain injury, especially in terms of prognostication. Since the CEUS of the brain can be performed at bedside, serially if needed over the course of injury evolution, the technique can be of significant clinical value in caring for neonates and infants with brain injury. It will be important to validate the initial evidence from early CEUS

---

brain scanning studies, and establish standardized quantitative techniques to reduce interpretation variations and errors in the clinical research setting.

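### The quantitative endpoint is tied to MRI, but the only test named for comparing patients with controls is a Wilcoxon test, which does not estimate how well CEUS detects injury

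*Combined protocol and SAP*

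**What the plan says.** Section 6.2 defines the secondary endpoint as "Quantitative analysis of perfusion abnormalities in correlation with clinical MRI results", to be obtained from regions of interest and time-intensity curves. Section 6 repeats that abnormalities will be correlated with MRI as the gold standard, and allows a nuclear scan to take that place in the most severely injured infants. No correlation or agreement statistic is named, and no cut-off, sensitivity, specificity, ROC area, confidence interval or performance target.

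The method named for the patient-control data is in Section 6. Controls are infants suspected or at risk of HII who prove "normal on imaging and clinical evaluation) using non-parametric Wilcoxon testing". Section 6 also names a McNemar test of grayscale against contrast ultrasound and a paired Wilcoxon test of perfusion before and after resuscitation.

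Section 3.4 states: "It is expected 200 subjects will be enrolled to produce 100 evaluable subjects". Section 6.4 expects about half of them to be abnormal, "thus providing a final sample of approximately 50 patients with abnormal perfusion and 50 patients with normal perfusion", and concludes: "Power analyses indicate that the study is sufficiently powered to detect group perfusion differences". The Protocol Synopsis gives as rationale that CEUS "has the potential to improve sensitivity and specificity for a variety of neonatal neurological diseases".

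**The concern.** The rationale is about the individual infant: whether a bedside CEUS reading identifies injury that MRI would show. A Wilcoxon p-value answers a different question, namely whether values in one group tend to be lower or higher than in the other. With 50 per group, a parameter that separates infants poorly and one that separates them well can both be significant. The trial could then end without an estimate of the quantity that motivates it.

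The other named tests do not fill the gap. McNemar needs a positive or negative call per infant, and no rule turns wash-in rate, time to peak, peak intensity or area under the curve into one. The paired Wilcoxon test concerns change over time.

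The control definition adds to this. An infant with normal MRI but an abnormal clinical evaluation cannot be a control, and the plan does not say where such an infant goes. Leaving out these less clear-cut negatives would tend to flatter discrimination. Section 6.4 describes the two groups differently again, as abnormal and normal perfusion. If groups were formed that way, the comparison would be partly circular.

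**Working it through.** **Inputs.** Groups of 50 and 50, and alpha 0.05 (Section 6.4; sidedness is not stated, two-sided assumed). Planning values, control versus patient, from Section 6.4: basal ganglia PE 1.37 (SD 0.23) versus 0.96 (0.09); peak cortical perfusion 2.46 (1.96) versus 0.69 (0.20).

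**1. The plan's own power.** Power ≈ Φ(difference / √((s1² + s2²)/n) − 1.96).
- Basal ganglia, n = 50: 0.41 / (0.247/√50) = 11.7, so power is 1.00. With n = 25 the ratio is 8.3 and power is again 1.00. The stated value reproduces.
- Cortex, n = 50: 1.77 / (1.970/√50) = 6.35, so power is 1.00. The stated 0.84 and 0.85 do not reproduce. Pooled t, Welch and simulated Wilcoxon calculations also give 1.00. That is a separate matter, and nothing below depends on it.

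**2. Smallest significant result.** The Mann-Whitney statistic divided by n1·n2 is the observed ROC area. Its null SD is √((n1 + n2 + 1)/(12·n1·n2)) = √(101/30,000) = 0.058. The boundary is 0.5 + 1.96 × 0.058 = 0.614. At 25 versus 25 it is 0.5 + 1.96 × 0.0825 = 0.662.

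**3. Misclassification at that boundary (50 versus 50, both groups weighted equally).**
- Equal-variance normal data: d = √2 × Φ⁻¹(0.614) = 0.41, and the error at the midpoint cut is Φ(−0.41/2) = 42%.
- Normal data with the same ROC area, SD ratio 0.23 to 0.09, best single cut found numerically: 34%.
- The same with SD ratio 1.96 to 0.20: 24%.

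A true effect at d = 0.41 would be significant only about half the time (simulated power 0.51). At the true effect detected with 80% power (d about 0.57, equal variances), the error is still about 39%.

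**4. At the planned effects.** ROC area = Φ(difference / √(s1² + s2²)).
- Basal ganglia: Φ(0.41/0.247) = Φ(1.66) = 0.95; best single cut misclassifies about 9%.
- Cortex: Φ(1.77/1.970) = Φ(0.90) = 0.82; best single cut misclassifies about 13%.

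In simulation at 50 per group, the Wilcoxon test was significant in every run for both, so the p-value does not tell the two apart.

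**5. What an interval would show.** Hanley-McNeil: SE² = [A(1 − A) + 49(Q1 − A²) + 49(Q2 − A²)]/2500, with Q1 = A/(2 − A) and Q2 = 2A²/(1 + A).

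| ROC area | SE | Approximate 95% CI |
|---|---|---|
| 0.614 | 0.056 | 0.50 to 0.72 |
| 0.82 | 0.042 | 0.74 to 0.90 |
| 0.95 | 0.023 | 0.91 to 0.99 |

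The same 100 infants give clearly different answers once the area and its interval are reported.

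**The case against.** The strongest reply is that this is early work. Section 6 presents the sample as adequate for feasibility and for optimising the technique, and says that imaging plane and region placement are not settled. The objectives in Section 2 are to identify regions and to generate a mapping method. Sections 4.2.2 and 5 bar CEUS from directing care without confirmation by another established method. A group comparison is a reasonable secondary analysis at that stage. This stands, and it limits the consequence. It does not remove the gap, because Section 6.2 still makes the relation to MRI an endpoint and gives no statistic for it.

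A reader might also infer four stronger things that the documents do not support:
- That p < 0.05 is the success rule for the endpoint. Nothing says so, or that significance would demonstrate detection.
- That the patient-control Wilcoxon test is the only test in the plan. Section 6 names two others, although neither gives accuracy for the quantitative parameters.
- That 42% is the error to expect. It is a boundary value under equal variances, which the plan's own SDs contradict.
- That Section 6.4 claims power for diagnostic accuracy. It refers only to group differences.

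On controls, it is fair that they come from the clinical at-risk population and are not healthy volunteers. The documents do not say how many infants have normal MRI with an abnormal clinical evaluation, so the size of any bias cannot be stated.

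**Conclusion.** The concern holds as a gap in specification. The quantitative endpoint is defined against MRI, but no named analysis estimates how well a quantitative parameter separates infants with an abnormal reference result from those with a normal one. Significance at 50 versus 50 is compatible with an observed ROC area as low as about 0.61, where the best single cut misclassifies about 24% to 42% of infants depending on the SD ratio. If the planning values are right, performance would be much better (about 9% and 13% misclassified), but the planned test would not show that either.

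The ROC boundary assumes a two-sided test, 50 per group and the large-sample approximation. The error rates also assume normal data, which is doubtful for the cortical controls: a mean of 2.46 with SD 1.96 puts zero only 1.26 SDs below the mean. The change is worth making before analysis. It does not call the data collection into question.

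**What to change.** In Sections 6 and 6.2:
- Name one parameter and region, for example basal ganglia PE or the basal ganglia to cortex ratio, both of which Section 6.4 uses. Name one CEUS exam per infant, the one nearest the MRI.
- Report the ROC area with a DeLong 95% CI against the reference result, abnormal versus normal. The reference is MRI, or the nuclear scan where Section 6 lets it replace MRI, so that the most severely injured infants are not lost. Include every infant with a reference result, whatever the clinical evaluation.
- Add sensitivity and specificity with 95% CIs at a cross-validated cut-off.
- Add a supportive analysis of absolute deviation from the median of the reference-normal infants. Section 1.1 describes both reduced and increased flow after injury, and a one-direction ROC area, like the Wilcoxon test, can miss a parameter that moves both ways.
- Base any statement that quantitative CEUS detects injury on these intervals, and keep the Wilcoxon p-value as descriptive.

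Section 6.4 needs only a note that its power does not refer to diagnostic accuracy.

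No new subjects, scans or procedures are needed. The ROC area is the Mann-Whitney statistic divided by n1·n2, so it comes from the same data. The cost is committing in advance to one parameter and one exam, a little more analysis, and a claim that may look less favourable than a small p-value.
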